## **APPROACH**

The study will be conducted at the division of Endocrinology, Saint Louis University. Young males between the ages of 18-45 years will be recruited for the study. A total of 90 males will be recruited: 30 obese males (defined as  $\geq$ 30 kg/m^2) with HH, 30 obese males with normal FT concentrations and 30 lean males (<25 kg/m^2) with normal FT concentrations.

**Hypogonadal males:** 30 male subjects with HH will be recruited into the study. HH will be defined as subnormal FT concentrations along with normal or low LH concentrations ( $\leq$ 10 IU/L). We will define subnormal FT as <6.5 ng/dl. Subjects with subnormal FT and high LH (>10 IU/L) will not be recruited into the study. Obese subjects will be randomized to receive clomiphene or placebo (15 subjects each) thrice a week for 12 weeks.

**Eugonadal men:** 30 obese and 30 lean males with normal FT ( $\geq$ 6.5 ng/dl) will also be recruited in the study to serve as comparison groups. They will not be treated clomiphene.

**INCLUSION CRITERIA FOR THE STUDY:** Males with age 18-45 years inclusive will be recruited. Subjects with type 2 diabetes on anti-hyperglycemic drugs (including insulin) will be allowed as long as they are on stable doses of these compounds for at least 6 weeks. The doses of anti-hyperglycemic can be changed if the subject has hypoglycemia or hyperglycemia. A record of all the changes in the doses of the anti-diabetic drugs will be kept.

**EXCLUSION CRITERIA FOR THE STUDY:** 1) Use of androgens, clomiphene, hCG, aromatase inhibitors or over the counter health supplements which contain androgens currently or in the past 6 months; 2) Hematocrit > 50%; 3) Congestive heart failure; 4) currently suffering from depression; 5) type 1 diabetes; 6) Hepatic disease (transaminase > 3 times normal) or cirrhosis, or a history of liver dysfunction; 7) Renal impairment (eGFR < 30 ml/min/1.73m^2); 8) HIV or Hepatitis C positive status; 9) Participation in any other concurrent clinical trial; 10) currently suffering from foot ulcer, significant periodontal disease or any other chronic infectious condition 11) known allergy to clomiphene 12) uncontrolled adrenal or thyroid dysfunction 13) presence of an organic intracranial lesion e.g. pituitary tumor 14) history of cataracts 15) history of venous thromboembolic disease (i.e. deep vein thrombosis or pulmonary embolism).

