### **STUDY DESIGN:-**

**Screening Day (part of study):** All subjects will have completed the following procedures prior to participating in the study:-

1) Medical History; 2) Physical Exam: testicular volume will be measured by an orchidometer (38); 3) Informed consent; 4) Baseline lab (30 ml) draw to measure CBC, comprehensive metabolic panel (CMP that includes liver and kidney function tests), total and free T, SHBG, LH and FSH. All labs will be drawn in the fasting state in the morning before 10am. All laboratory samples will be tested in the Endocrine laboratory in Doisy Hall Room 204.

**Study visits for males with normal FT:** The participants will come fasting and have blood drawn for research labs (insulin, glucose, inflammation). They will then be discharged from the study.

**Study visits for obese males with HH:** These subjects will enter a double blind randomized placebo controlled trial. Subjects who qualify and consent to take part in the study will be assigned a number by a computerized random number generation program and will be randomized (1:1) to receive either clomiphene or placebo. An unblinded research nurse and pharmacist will administer study product, all other investigators and the study participants will be blinded. This number will be used as the study subject ID. A master list of subject name and study ID will be kept under lock and key to protect patient identifiers. Only the assigned research nurse will have access to the randomization list.

**1. Visit day 0:** The participants will come fasting and have blood drawn for research labs (insulin, glucose, CRP; 45 ml). Waist circumference will be measured. They will be given a supply of clomiphene or placebo pills containing cellulose. Clomiphene citrate is available as 50 mg tablets and has a half life of 5-7 days. The starting dose of clomiphene will be 25mg on Monday, Wednesday and Friday mornings. All subjects will be given a pill container that will have separate boxes for different days of the week.

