**Data Analysis:** The focus of the proposed research is to evaluate the efficacy of clomiphene treatment on T concentrations in young obese post-pubertal males. Transformations of the data in order to meet statistical assumptions may be considered. The results will be computed as mean  $\pm$  standard deviation (SD). The primary endpoint of the study is to detect a difference in FT concentrations after treatment with clomiphene for 12 weeks. There are no prior studies analyzing the effect of clomiphene in young males with HH. However, studies in middle aged men with obesity related HH and use of clomiphene or its isomer, enclomiphene have shown an increase in FT concentrations by 150%(21, 43). Change in FT concentrations following clomiphene or placebo for 12 weeks will be compared among the groups by unpaired *t*-test. Conservatively estimating a difference in FT concentrations of 50%, a sample size of 15 patients per treatment group (assuming a drop-out rate of 20%) should provide adequate power( $\beta = 0.8$ ) to detect a significant difference ( $\alpha = 0.05$ ), provided the standard deviation of the residuals is not greater than 40%. Thus 30 obese subjects with HH (15 patients each in clomiphene and placebo groups) will be sufficient. For baseline comparisons with men without HH, we will recruit 30 eugonadal obese and 30 lean males. Thus there will be 90 subjects in the study.

**Secondary End Points:** The secondary endpoints for the study will be comparison of the relative change from baseline in HOMA-IR and inflammatory mediators after clomiphene or placebo. These parameters will also be compared between obese and lean males at baseline. We have previously shown that obese men with HH have 36% higher insulin resistance than eugonadal men. Estimating a difference in HOMA-IR of 20%, a sample size of 30 patients per treatment group should provide adequate power( $\beta = 0.8$ ) to detect a significant difference ( $\alpha = 0.05$ ), provided the standard deviation of the residuals is not greater than 25%.

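### Type 2 diabetes is neither a stated randomisation stratum nor a covariate in the randomised HOMA-IR and inflammation comparisons; adding both is a cheap gain in precision

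*Combined protocol and SAP*

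**What the plan says.** - **Allocation** (STUDY DESIGN, study visits for obese males with HH): participants are "assigned a number by a computerized random number generation program and will be randomized (1:1) to receive either clomiphene or placebo". A list exists: "Only the assigned research nurse will have access to the randomization list". How it is built is not described. Blocking, block size, stratification and minimisation are neither mentioned nor excluded.
- **Arm sizes:** APPROACH states "Obese subjects will be randomized to receive clomiphene or placebo (15 subjects each) thrice a week for 12 weeks", and Data Analysis repeats it: "Thus 30 obese subjects with HH (15 patients each in clomiphene and placebo groups) will be sufficient".
- **Diabetes** (APPROACH, inclusion criteria): "Subjects with type 2 diabetes on anti-hyperglycemic drugs (including insulin) will be allowed", given stable doses for at least 6 weeks beforehand. Doses may then change for hypo- or hyperglycemia. Changes are recorded, but no analysis is said to use them.
- **Endpoints** (Laboratory measurements; Data Analysis; Secondary End Points): HOMA-IR is the product of fasting insulin and fasting glucose divided by 22.5. HOMA-IR and the inflammatory mediators are secondary endpoints, analysed as relative change from baseline. The one between-arm test named is an unpaired t-test, for free testosterone (FT). No covariate is given for any comparison.

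**The concern.** HOMA-IR is built from the two quantities that diabetes and its drugs act on most directly. In a trial of 30 men the diabetic patients can fall unevenly between arms by chance, and the plan as written deals with this neither at allocation nor in the analysis. Analysing relative change offsets differences in baseline level. It does not offset a different response in diabetic men, or dose changes made during the 12 weeks.

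What is at stake is the precision and readability of the randomised HOMA-IR and inflammation results. An avoidable part of their noise would come from a factor that is known before randomisation, and a visible diabetes imbalance would leave the result open to argument.

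**Working it through.** **1. The plan's own figure.** Inputs from Data Analysis: "Conservatively estimating a difference in FT concentrations of 50" per cent, "provided the standard deviation of the residuals is not greater than 40" per cent, and "a sample size of 15 patients per treatment group (assuming a drop-out rate of 20" per cent). With two-sided alpha 0.05 (sidedness assumed) and the noncentral t, the smallest arm giving at least 80% power is 12 (power 83.3%), and 12/0.8 = 15. The stated size reproduces.

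**2. Does the split matter for the primary endpoint?** Suppose allocation were a simple coin toss. The number in one arm is then Binomial(30, 0.5). Exactly 15:15 occurs in 14.4% of trials, and 20:10 or worse in 9.9%. Power with 20% drop-out:

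| Split | 15:15 | 18:12 | 19:11 | 20:10 |
|---|---|---|---|---|
| Power | 83.3% | 81.8% | 80.5% | 78.8% |

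Averaged over all splits, power is 82.0%, a loss of 83.3 − 82.0 = 1.3 points.

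**3. Diabetes balance with 15:15 held.** Let D of the 30 men be diabetic (assumed 9 to 15) and x of them fall in one arm. Then x is hypergeometric (30, D, 15), and the arms differ by |2x − D| diabetic men.

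| D | Differ by 4 or more, 15:15 held | Same, simple allocation |
|---|---|---|
| 9 | 10.9% | 18.0% |
| 12 | 26.4% | 38.8% |
| 15 | 14.3% | 30.2% |

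With 15:15 held and D odd, the difference is always odd, so 4 or more means 5 or more. That is why the middle row is highest.

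**4. Effect on the HOMA-IR arm difference.** Let g be the difference in mean relative change between diabetic and non-diabetic men (assumed 20 points, range 10 to 30). The chance shift is g(2x − D)/15, with

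SD = g × (2/15) × √[15 × (D/30) × (1 − D/30) × (15/29)].

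- D = 9: 20 × (2/15) × √1.629 = 3.4 points.
- D = 12: 20 × (2/15) × √1.862 = 3.6 points.
- D = 15: 20 × (2/15) × √1.940 = 3.7 points.

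At g = 10 the SD is 1.7 to 1.9, and fewer than 1% of trials shift by 5 points or more. At g = 30 it is 5.1 to 5.6.

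**5. Set against the standard error.** With the plan's HOMA-IR SD of 25%, the standard error is 25 × √(2/15) = 9.1 points at 15 per arm and 25 × √(2/12) = 10.2 at 12. The shift in step 4 lies inside this figure. At g = 20 it makes up 3.4²/9.13² = 14% to 3.71²/9.13² = 17% of the variance.

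**6. What the change buys.** Take the 25% SD as including the diabetes component. Removing it leaves a variance of 625 − g²p(1 − p), where p = D/30. At g = 20:

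- D = 9: 625 − 84 = 541, standard error √541 × √(2/15) = 8.5.
- D = 15: 625 − 100 = 525, standard error √525 × √(2/15) = 8.4.

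These hold when diabetes is balanced. Adjustment after unstratified allocation inflates the variance by about 4% on average, a factor of √1.04 = 1.02 on the standard error, giving about 8.5 to 8.7. At g = 10 the balanced figure is 8.9 to 9.0, and adjustment alone gains nothing material.

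Stratified blocks of four cut the shift SD at g = 20 to 0.6 to 1.0 points. Because of incomplete blocks, they give exactly 15:15 in about 50%, 67% and 50% of trials for D = 9, 12 and 15, and otherwise 16:14, where primary power is 83.1%.

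**The case against.** The best counter-argument is that chance imbalance is not bias. Randomisation makes it part of the sampling error the test already allows for, and 3.4 to 3.7 points sits inside a standard error of about 9. This is correct, and it limits the point to precision.

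The sizes also rest on two assumptions the documents do not supply: the diabetic share, and the difference in relative change by diabetes status. At 10 points the problem is negligible. This also stands.

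The randomised HOMA-IR comparison is limited far more by its size. The 20% difference and 25% SD in the plan are tied to 30 per group. With 12 to 15 per arm, power for 20% is about 47% to 56%. This stands too, although it is a reason to take any inexpensive precision on offer.

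A reader might go further and infer three things that the documents do not support:

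- **That the 15:15 split is left to chance and primary power is in danger.** The plan is silent on blocking and does not exclude it. It fixes 15 per arm twice and refers to a list, so a list built to give 15 and 15 fits every sentence. Even under simple allocation the mean loss is 1.3 points, and power drops below 80% only at 20:10 or worse.
- **That the HOMA-IR comparison would be biased.** It would be noisier, with no systematic direction.
- **That an imbalance could not be repaired afterwards.** Adjusting for one binary factor in 30 men costs about 4% in variance on average.

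**Conclusion.** The point holds as a low-to-moderate improvement for secondary endpoints, not as an error in the plan. Diabetes is admitted, bears directly on HOMA-IR, and is controlled neither in the stated allocation nor in the stated analysis. This is true whether or not 15:15 is enforced.

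Under the central assumptions (9 to 15 diabetic men, a 20-point difference in relative change), stratifying and adjusting would lower the HOMA-IR standard error from about 9.1 to about 8.4 to 8.5 points. Adjustment alone would reach about 8.5 to 8.7. The gain disappears if the difference is near 10 points and grows if it is near 30. No size was worked out for the inflammatory mediators, for which the documents give no SD.

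**What to change.** 1. In STUDY DESIGN, describe the list: computer-generated, permuted blocks, 1:1, stratified by type 2 diabetes (yes/no), with block sizes that vary and are not disclosed to enrolling staff.
2. In Data Analysis and Secondary End Points, include diabetes status as a factor in the randomised HOMA-IR and inflammation comparisons.
3. If the list has already been made, do step 2 alone and state how the existing list was built. That recovers most of the gain.

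The cost is a sentence in each place and a two-stratum list, with no extra patients or visits. The downsides are one degree of freedom, slightly more predictable late allocations for anyone who knows the earlier ones, and incomplete blocks that may leave the total slightly off 15:15.

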**2. Visits to adjust study drug (week 4 and week 8):** A blood sample (30 ml) will be collected at weeks 4 and 8 to measure CBC, CMP and FT concentrations. The time frame for follow-ups will be within a week of the designated follow up time. Dose of clomiphene will be adjusted to keep FT between 12 and 16 ng/dL (mid-normal for healthy young men). If FT is <12 ng/dl, then the dose of CC will be increased by 25mg/week. If FT is >16 ng/dl, then the dose will be reduced by 25mg/week. The blood samples for dose adjustment will be taken on Wednesday or Friday. Patients in both clomiphene and placebo groups will be told that their tablet quantities may vary during the study. If the number of pills of a patient in the clomiphene group is changed, a similar change will be made in the number of placebo tablets in the next patient in placebo group.

**3. Week 12:** The participants will come fasting and have blood drawn for research labs, CBC, CMP, SHBG, LH, FSH total and free T (45 ml). Waist circumference and testicular size will be measured. Gynecomastia will be assessed. Subjects will then be discharged from the study.

The following study termination criteria will be applied:-

- Adverse events considered by the PI to be associated with the use of the study drug
- Suspected thromboembolic event, including pulmonary embolism. Subjects who have a thromboembolic event ruled out may reinstate treatment
- Hemoglobin of 18 g/dL or higher, or a hematocrit of 54% or higher
- Visual changes which may be prolonged and possibly irreversible. Subjects will be advised to stop drug and be referred to an ophthalmologist.
- The subject requests to be withdrawn from the study

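### The one screening FT that selects men is also the baseline for the primary change in FT; a day-0 FT would cheaply remove regression to the mean from within-arm changes

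*Combined protocol and SAP*

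**What the plan says.** **Selection (Approach, Hypogonadal males).** "HH will be defined as subnormal FT concentrations along with normal or low LH concentrations", and "We will define subnormal FT as <6.5 ng/dl". No repeat or confirmatory FT is mentioned.

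**Screening (Study Design, Screening Day).** One blood draw, described as "Baseline lab (30 ml) draw to measure CBC" and further tests, among them "total and free T, SHBG, LH and FSH. All labs will be drawn in the fasting state in the morning before 10am". This is the only draw on which the 6.5 ng/dl rule can be applied.

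**Day 0 (Study Design, Visit day 0).** "The participants will come fasting and have blood drawn for research labs (insulin, glucose, CRP; 45 ml". FT, total T, SHBG, LH and FSH are not listed. No maximum interval between screening and day 0 is given.

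**After treatment starts.** "A blood sample (30 ml) will be collected at weeks 4 and 8 to measure CBC, CMP and FT concentrations". At week 12, total and free T are listed again, as items separate from the research labs.

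**Analysis (Data Analysis).** "The primary endpoint of the study is to detect a difference in FT concentrations after treatment with clomiphene for 12 weeks", and "Change in FT concentrations following clomiphene or placebo for 12 weeks will be compared among the groups by unpaired *t*-test". No baseline covariate is named.

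**The concern.** A value picked because it fell below a cut-off is, on average, lower than the man's usual level whenever there is any within-man or assay variation. His next value then tends to be higher with no treatment at all. Here that selected value is also the starting point for the change in FT.

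Three things are exposed:

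- **Within-arm FT change.** Both arms' rises are inflated. The Significance section says the trial will supply early efficacy evidence for planning later trials and for setting beside other treatments. A percentage rise lifted from the clomiphene arm for that use would include the artefact.
- **The HH label in Aim 1.** The comparison of obese men with and without HH rests on one FT per man and has no randomisation to protect it. Men whose usual FT lies on the other side of the cut-off would tend to dilute the contrast.
- **Precision.** A single noisy baseline adds variance to every change score in a trial with 15 men per arm.

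**Working it through.** **1. The plan's own figure.** Inputs from Data Analysis: difference 50%, SD 40%, alpha 0.05 (two-sided assumed), power 0.8, drop-out 20%. Standardised difference = 50/40 = 1.25. A two-sample t-test needs 11.09, so 12 per arm, and 12/(1 - 0.20) = 15, as stated. Power is 83% with 12 completers per arm and 91% with 15. Nothing below changes this sample size.

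**2. Is FT drawn on day 0?**

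| Visit | FT listed? |
|---|---|
| Screening | Yes, and it decides entry |
| Day 0 | No; insulin, glucose and CRP named |
| Weeks 4 and 8 | Yes |
| Week 12 | Yes, separately from research labs |

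Laboratory measurements places T and FT with the commercial laboratory, not among the research-laboratory assays. The natural reading is that the day-0 research labs do not include FT.

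**3. Size of the untreated rise and of mislabelling.** The documents give no FT distribution and no within-man CV, so these are assumptions: true FT in screened obese men is normal with mean 7.5-9 and SD 2-2.5 ng/dl, and each measurement is true FT × (1 + error) with CV 10-20%. Simulate 1,000,000 men per scenario and keep those whose first value is below 6.5. Then:

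- untreated rise = mean of a later value - mean of the first value
- mislabelled share = proportion with true FT of 6.5 or more

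| True mean, SD, CV | Mean first value | Untreated rise | % of baseline | True FT ≥6.5 |
|---|---|---|---|---|
| 7.5, 2.5, 10% | 4.86 | 0.19 | 4% | 13% |
| 9, 2.5, 15% | 5.15 | 0.65 | 13% | 31% |
| 9, 2, 15% | 5.45 | 0.89 | 16% | 44% |
| 9, 2, 20% | 5.32 | 1.51 | 28% | 56% |

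Over the whole grid the rise is about 4-28% of baseline (about 9-16% at CV 15%) and the mislabelled share is 13-56% (20-44% at CV 15%). The mislabelled men have an average true FT of about 7.0-8.0 ng/dl, that is 0.5-1.5 above the cut-off. Measured from a day-0 FT not used for selection, the expected untreated rise is zero. Measured from the mean of the two values, about half remains (0.33 of 0.65 in the second row).

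**4. Is the between-arm test affected?** With mean 8, SD 2.5, CV 15% and no treatment effect, placebo FT still rises about 0.49 ng/dl (about 10%). The between-arm difference is about 0, and the unpaired t-test rejects in 4.9-5.0% of runs with 12 or 15 per arm.

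**5. Precision gain at the plan's SD.** In untreated men with mean 9, SD 2.5 and CV 15%, averaging two baselines lowers the SD of change from 1.36 to 1.13. The plan allows a residual SD of 40%, read here as 40% of baseline: 0.40 × 5.15 = 2.06. Other variance = 2.06² - 1.36² = 2.39. With the two-value baseline the SD is √(2.39 + 1.13²) = 1.92, a cut of 1 - 1.92/2.06 = 7%. Over the grid the cut is about 2-16% (5-7% at CV 15%), and it is about the same when the mean of the two values is used as a covariate.

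**The case against.** **No planned test uses the inflated quantity.** The primary analysis compares change between arms that were selected identically. No within-arm FT test is specified, and the 150% rise cited in Data Analysis is only background to the planning effect. This stands. A reader might infer that the primary treatment effect is biased or its type I error inflated; step 4 shows that neither follows.

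**Hypothesis 2 is not about FT.** A reader might infer that the artefact undermines the claim that clomiphene reverses the abnormalities. The abnormalities named there are Leydig and Sertoli cell function, insulin sensitivity and inflammation. They are measured by other markers, none of which selects men, so selection on FT does not directly set their baselines. This stands.

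**Adjoining cut-offs.** A reader might also fault the HH and eugonadal definitions for meeting at 6.5 ng/dl. The plan defines the groups by measured FT, and a gap would be a design preference, not a correction.

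**The day-0 list may not be exhaustive.** It also omits insulin-like factor 3, inhibin B, FFA and TNF-alpha, whose baselines the aims need. In addition, Screening Day sends all samples to the in-house Endocrine laboratory while Laboratory measurements sends FT to a commercial one; these should be reconciled. A day-0 FT is therefore not excluded, but the separate FT listing at week 12 makes it unlikely. If one is intended, the protocol should say so.

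**The size is assumed.** This stands. The range is wide, and fasting draws before 10am and LC-MS/MS with equilibrium dialysis limit the noise. The direction, however, holds for any non-zero variation.

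**Conclusion.** The point holds in a limited form. On the natural reading of the schedule, one FT value both selects the man and serves as his baseline. This leaves the randomised comparison and the sample size intact. It inflates each arm's own FT change and blurs the HH label in Aim 1. The figures of about 4-28% for the untreated rise and 13-56% for mislabelling rest entirely on the assumed FT distribution and CV; the documents can neither confirm nor narrow them.

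The gain in precision from a second baseline is modest at the planned SD. The larger reduction seen in untreated men (from 1.36 to 1.13 in the worked case) should not be expected in the trial, where variable response to treatment adds to the variance. Low severity, but worth doing because it is cheap and because a missed pre-dose FT cannot be recovered later.

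**What to change.** 1. Add FT, and preferably total T, SHBG, LH and FSH, to the fasting pre-dose day-0 sample. Keep screening FT for eligibility.
2. Report within-arm FT change from day-0 FT only, not from the mean of the two values.
3. In the between-arm primary analysis, adjust for the mean of screening and day-0 FT, or for both values, as covariate.
4. For Aim 1, add a sensitivity analysis restricting the HH group to men whose day-0 FT is also below 6.5 ng/dl. State that eugonadal men have no second FT, so only one side of the cut-off is checked.

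**Cost:** about 30 extra assays (or panels) on blood already being drawn, and short additions to the visit schedule and Data Analysis. No extra visit or staff, and no change to 15 per arm. The reported within-arm rise will look slightly smaller.

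### Low-priority safety improvement: randomised men are discharged at week 12 with most of the last clomiphene load probably still present, and no contact is scheduled during the washout

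*Combined protocol and SAP*

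**What the plan says.** All references are to the combined protocol and SAP.

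- **Treatment (APPROACH, hypogonadal males):** "Obese subjects will be randomized to receive clomiphene or placebo (15 subjects each) thrice a week for 12 weeks".
- **Drug and dose (STUDY DESIGN, visit day 0):** on the half-life, "Clomiphene citrate is available as 50 mg tablets and has a half life of 5-7 days". Men begin on 25 mg three mornings a week. At weeks 4 and 8 the weekly dose may go up or down by 25 mg according to FT.
- **Last contact (STUDY DESIGN, week 12):** blood is drawn, including CBC and CMP, and waist and testicular size are measured. Then: "Gynecomastia will be assessed. Subjects will then be discharged from the study".
- **Termination criteria (STUDY DESIGN):** these include suspected thromboembolism, hemoglobin of 18 g/dL or hematocrit of 54% and above, and visual changes. For thromboembolism, "Subjects who have a thromboembolic event ruled out may reinstate treatment". For vision: "Visual changes which may be prolonged and possibly irreversible. Subjects will be advised to stop drug and be referred to an ophthalmologist".
- **Exclusions (APPROACH):** among others, "history of venous thromboembolic disease", past cataracts and hematocrit above 50%.

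The text available for review describes no visit, call or adverse-event window after week 12, and sets no washout period for this trial.

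**The concern.** Observation stops when dosing stops, but exposure does not. With a half-life of 5-7 days and dosing three times a week, a man on clomiphene leaves the study with drug still in his body. A man on placebo does not.

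The plan treats two harms as serious enough to end treatment, and says of one that it may persist or be irreversible. A thromboembolic or visual event that begins during the washout has no scheduled route into the study record.

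There is a smaller, related gap. A blood count is taken at the discharge visit, but the hemoglobin and hematocrit limits are written as rules for stopping treatment, and treatment is ending anyway. The text gives no action for a week-12 value above the limit.

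At stake are the safety of individual men and a complete harm record in a study that is meant to inform later trials. No efficacy result is at stake.

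**Working it through.** The plan gives no washout or post-treatment figure, so there is none of its own to reproduce. The check applies first-order elimination to the plan's half-life.

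**Inputs**
- Half-life h = 5 to 7 days (STUDY DESIGN, visit day 0).
- Dosing on Monday, Wednesday and Friday at 25 mg, i.e. 75 mg/week at the start, for 12 weeks (STUDY DESIGN; APPROACH).
- Gap g from last dose to week-12 visit: not stated. Assumed 1-3 days, because the schedule leaves intervals of 2, 2 and 3 days between doses.

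**1. Load at discharge**, as a share of the level just after the last dose: R(g) = 2^(-g/h).

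| Gap | h = 5 days | h = 7 days |
|---|---|---|
| 1 day | 2^(-1/5) = 87% | 2^(-1/7) = 91% |
| 3 days | 2^(-3/5) = 66% | 2^(-3/7) = 74% |

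The range is 66-91%. These shares do not depend on the dose reached by titration.

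**2. Length of washout**
- Four half-lives: 4 × 5 = 20 to 4 × 7 = 28 days, or 2.9-4.0 weeks.
- Decline to 5%: h × log2(20) = 5 × 4.32 = 21.6 days to 7 × 4.32 = 30.3 days.
- Five half-lives: 25 to 35 days, or 3.6-5.0 weeks.

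The washout is therefore about 3-5 weeks, depending on the convention and the half-life.

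**3. Share of total exposure after discharge.** Assume a constant 75 mg/week: 36 doses of 25 mg, total 900 mg, first dose on a Monday (day 0), last dose on day 81. Under first-order elimination the share of AUC still to come is the drug remaining divided by the cumulative dose.
- Visit on day 82 (1-day gap): 81.7/900 = 9.1% (h = 5) and 112.9/900 = 12.5% (h = 7).
- Visit on day 84 (3-day gap): 61.9/900 = 6.9% and 92.6/900 = 10.3%.

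So about 7-13% of exposure falls after the last contact.

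**4. Timing of a call.** At 35 days after the last dose, 2^(-35/5) = 0.8% to 2^(-35/7) = 3.1% of the post-dose load remains. At 21 days it would be 5.4% to 12.5%. A call at about 5 weeks spans the washout at either end of the half-life range; one at 3 weeks does not.

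**The case against.** The case against giving this much weight is good, and most of it stands.

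- **It is an improvement, not an error.** Nothing in the plan is contradicted or miscalculated. Conceded.
- **The yield is small.** Load only falls after the last dose, and the plan watches the period of highest load. The documents give no event rate. As an illustration only, assume that 1-5% of the 15 clomiphene men have a relevant event per course, with risk proportional to exposure. Then 15 × 0.01 × 0.069 = 0.01 to 15 × 0.05 × 0.125 = 0.09 events fall after discharge. With the plan's 20% drop-out, about 15 × 0.8 = 12 men, not 15, would reach that visit.
- **Safeguards exist.** The exclusions, a low dose titrated to mid-normal FT, and CBC/CMP at weeks 4, 8 and 12 all reduce the risk. On-treatment visual changes lead to ophthalmology referral, and restarting after a thromboembolic event is ruled out implies a work-up.
- **Silence is weak evidence.** The consent pages were removed from the text available here and may tell men to report later symptoms. That limits the point to scheduled contact; it does not remove it, because a scheduled call gathers the same information from both arms.
- **One half-life for two isomers.** The background describes clomiphene as a mixture of isomers with different actions, but the plan gives only one half-life range. If one isomer clears more slowly, the washout is longer than shown.
- **On-treatment questioning matters more.** The text sets out no systematic adverse-event questions at weeks 4, 8 or 12 either. True, but that is a separate matter.

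A reader might also extend the visit window ("The time frame for follow-ups will be within a week of the designated follow up time") to week 12 and suppose a late visit well after the last dose. That sentence stands under the week 4 and week 8 visits, and nothing says that dosing stops on schedule if the week-12 visit is late. No such scenario is used here.

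**Conclusion.** The point holds as an optional, low-priority safety improvement. Men on clomiphene probably leave the study with about 66-91% of the post-dose load, and no contact is scheduled over the next 3-5 weeks. This rests on the plan's 5-7 day half-life, first-order elimination and an assumed gap of 1-3 days between last dose and visit. The expected number of missed events is small and cannot be computed from the documents.

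Two stronger conclusions are not supported:

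- A reader might infer that events still open at week 12 are abandoned. The plan does not say so. It uses the same discharge wording for untreated controls after their blood draw, so it may mark only the end of scheduled visits.
- A reader might infer that one telephone call closes the gap. It would collect symptoms, but not laboratory findings such as a high hematocrit, which need a repeat blood count.

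The FT endpoint, sample size, power and efficacy analysis are not affected.

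**What to change.** Keep week 12 as the end of treatment and the FT endpoint visit. Replace the discharge sentence for randomised men with:

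> Every randomised man, in both arms, is telephoned about 5 weeks after his last dose and asked about visual, thromboembolic and other adverse events. Any open event, or a week-12 hemoglobin of 18 g/dL or hematocrit of 54% or above, is followed until it resolves or stabilises. He is then discharged.

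The call goes to both arms so that it reveals nothing about allocation. Timing it from the last dose also covers men who stop treatment early. If the consent form already provides equivalent active follow-up, a cross-reference in the protocol is enough.

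**Cost:** about 30 calls, an occasional repeat CBC, about 5 more weeks of participation per man, and a short protocol and consent amendment.
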